Outpatient Bipolar Clinic. After running data queries using the study's inclusion and exclusion criteria, we will request detailed data through RPDR in order to directly contact those patients who are eligible for the study and who have consented to be contacted in future for research purposes. Detailed data requests, including identifying information such as medical information and contact information, will be approved by the Partners IRB.

Random (1:1) allocation: We will assess eligibility, NP's will conduct the informed consent process, then randomize eligible subjects to one of two arms: 1) fixed-dose statin and/or ARB; or 2) usual treatment with greater monitoring. In both arms, the patient's clinical care remains within the original mental health clinics. We will use a computerized random number generator. Participants unable to be randomized due to eligibility issues discovered at the first study visit will still be followed as not-randomized subjects.

Randomization scheme: We will start with a concealed, simple subject-level randomization scheme, e.g., web or telephone delivered random sequence. [104-106] We also will consider concealed, block randomization schemes, e.g., accounting for clinic and time with randomly varied block sizes. An investigator not involved in the arm assignment or clinical care of subjects will perform the generation and allocation concealment.

Intervention: The multi-component intervention exploits a number of strategies from incentive theory and behavioral economics, including: a) a simplified drug regimen; b) free treatments; c); framing of goals and goal setting; and d) focus on immediate cardiovascular risks within a larger plan for risk reduction.^[107-114]

Control: We will compare the initial treatment intervention with usual treatment (control arm), with both arms superimposed on a system of regular monitoring base. The RA/APRN pair will make no effort to alter or influence treatment or use of that treatment for subjects in the control arm. Note that our goal in the Control arm is to characterize "usual treatment". We will not intervene in this care except in emergencies requiring us to notify the patient's treatment team. Some patients who need care for metabolic syndrome may not be receiving it – just as they would if not in our trial.

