Follow-up: Up to 24 months. We will censor subjects (from the intervention) who receive a diagnosis of diabetes, when they develop a cardiovascular or cerebrovascular event, who die, or who leave the study health care systems. During each follow-up visit, the study nurse will review all prescription drugs and the RA will perform pill counts of cardiovascular drugs (we will ask subjects to bring all of their drugs in to each study visit). The study nurse will perform safety checks comparable to that during baseline evaluation. For subjects in either arm identified during our safety checks or who have events, we will recommend that they receive more intensive care from primary care physicians, cardiologists, or endocrinologists, and will message their clinicians. We will continue to monitor these subjects throughout the follow-up period albeit now on a more intensive treatment regimen.

At the end of the study, we will characterize the clinical care for subjects in both study arms, thus providing a detailed description of "usual treatment," and information about care received from other clinicians for subjects in the intervention arm. We will report on all clinicians seen (specialty, location, visit frequency and timing), conditions diagnosed and treated (psychiatric and medical), and cardiovascular conditions diagnosed and treated (major events such as ED visits or hospitalizations, diagnoses, drugs, doses). We will compile adverse events using the CATIE adverse event reporting tool as a base.^[115]

Subjects will have the option to continue coming to follow-up visits after the 12-month endpoint every 6 months for another 12 months. We will not continue to prescribe medicine to subjects in the intervention arm, rather we would continue to collect data so we can get a longer-term picture of "usual treatment" for those in each study arm (including non-randomized). RAs will perform pill counts at these additional follow-up visits, to get information about medication adherence for an additional year. NPs will continue to draw blood and ask subjects about their medications and medical history. Participants who have already signed consent and would like to participate in the post-study year of follow-up visits, will be asked to the new consent form prior to starting study procedures.

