Obtaining Study Drugs: Study nurse practitioners will prescribe study medication for subjects as follows: simvastatin 20 mg once per day, and/or losartan 25mg once per day or atorvastatin 10mg once per day and/or valsartan 40 mg once per day. The grant will pay for study medications at no cost to participants. The McLean Hospital Research pharmacy will procure the study medication for all study sites and dispense prescriptions in 3 month supplies. The study staff will pick up prescriptions from the pharmacy and provide to the subject during the study visit. Since the medications will be provided the same day, investigators will not store medications in any way, other than to transport the mediations to the various study sites. Study staff will follow the same procedures for procuring and dispensing medications at all external sites. That is, study staff will procure medications from The McLean Hospital Research pharmacy the morning of external site visits and transport the medications to dispense at each site.

Additional Data Sources: There are other noteworthy data sources for this trial: 1) clinic records; 2) electronic health records for two clinics; 3) APCD. RAs will systematically review the visit schedules and local medical records from each clinic for each subject. Additionally, McLean is scheduled to roll out its electronic health record (Epic Systems) during the course of this study, which we have extensive experience using in other settings. These data sources will provide complementary data sources for cross-validation (e.g., pharmacy fills, see quality checks below) as well as longitudinal information on psychiatric visit adherence, primary care visit frequency, and major unfavorable clinical events, e.g., ED visits and hospitalizations for psychiatric or cardiovascular events.

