Data Entry: We will use several strategies to augment and evaluate the quality of data entry: 1) standardized forms, e.g., for laboratory test orders, subject interviews, and

medical record data abstraction; 2) structured data entry through a secure, serverbased database system, e.g., MS Access; 3) double entry of standardized forms with routine error checks, e.g., every third subject; and 4) automated checks for value changes across observation points, e.g., sudden increase or decrease in symptom levels – flag values for additional review.

Additional Quality Checks: We also will perform complementary quality checks: 1) routine checks for missing values; 2) cross-validation of data (e.g., psychiatric symptom levels) by comparing study data vs. medical record information for a random sample of subjects; 3) cross-validation of adherence data: (a) self-report vs. (b) RA pill counts vs. (c) medical record (plus EHR/LMR for the two Partners clinics) vs. (d) APCD pharmacy records (both study arms – includes capture of any drugs prescribed by non-psychiatrists and/or dispensed by pharmacies);[135-137] and 4) periodic trend checks to identify and confirm large changes in any outcome or covariate values. During follow-up, we will ask any subjects who forget to bring their drugs to a visit for the pill count to bring their drugs in to their next clinical appointment for a "catch up" pill count. We will use a standardized process for addressing imputation of missing values or reconciliation of different values.

VI. Biostatistical Analysis

Analysis of Aim 1: Treatment: By design, all subjects in the Intervention arm will start by being under treatment. During the course of follow-up (FU), we expect that some will stay consistently on treatment, some will discontinue treatment (become non-adherent), while others will make transitions on and off treatment in various patterns (e.g., subsequent modifications made by any PCP and/or changes in adherence over time). In contrast, by design, subjects in the Usual Treatment (control) arm do not start on treatment; however, some will initiate treatment as a result of usual clinical care, e.g., PCP initiation. For this aim, in which we study treatment use at various time points, only an intent-to-treat (ITT) approach is relevant since whether or not subjects are on treatment is the outcome itself.

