For analysis of the repeated outcomes data, we will use econometric-style OLS linear model analysis of the repeated mean levels of the outcome over the five observation times (baseline + four follow-up times). This approach is robust to non-normal distributions. For constructing standard errors we will use cluster and heterogeneity robust estimation methods. Among estimation methods for this model, we will emphasize the use of the "fixed effects" (FE) option, which can be implemented in STATA using the xtreg command with the FE option. This essentially amounts to change score analysis that is generalized for use in situations with more than two repeated measures. This will provide estimates of the profiles of mean change from baseline in each of the treatment arms along with significance tests for contrasts between the two profiles. For plotting, the profiles of change will be anchored at the observed mean values in each arm at baseline. Inverse Probability (IP) weighting

methods will be used to account for possible endogenous loss to follow up in connection with the proposed analysis. Weighting will be based on baseline characteristics and for any given subject; the same weights will be applied to each repeated measure. We will finalize our analytic protocol before examining the outcome data, i.e., a priori delineation of the analytic protocol as is becoming the standard of analysis. We will use only marginal distributions to guide the appropriateness of the final choice of methods. Thus, we mitigate the potential for bias resulting from post-hoc choice of analysis or significance testing.

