Primary study outcome: The main outcome is use of the cardiovascular prevention medications over the 12-months after study initiation. For each individual, we define the primary outcome as the proportion of the 12 follow-up months during which she/he either received any of the prescribed medication or the medication became clinically contraindicated after trial entry (as decided by the treating physician). We will assess the outcome using medication counts at each study visit (i.e., at the 3-, 6-, 9-, and 12-month study visit), supplemented by subject self-reports and the clinic chart review. For subjects who are eligible to receive both statins and ARB medications at baseline, we will calculate the number of days that they receive both medications during the 12 months of follow-up. For subjects who are eligible to receive only one of the two medications at baseline (i.e., because of pre-existing therapy with or because of contraindications to the other prevention medication before trial entry), we will calculate the number of days that they receive the medication during the 12 months of follow-up, with the same approach for addressing changes in subsequent eligibility.

Analysis of the primary study outcome: The primary analysis will follow the intention-to-treat (ITT) principle. We will use regression analysis to estimate the mean average of the primary outcome in each group and the difference between the mean outcomes, along with its 95% confidence interval and using the p-value for a null hypothesis. If clinically meaningful imbalances are detected in baseline covariates despite randomization, we will adjust for those covariates. If necessary, we will adjust for selection bias due to loss to follow-up via inverse-probability weighting. In supplemental analyses to the main ITT approach, we also will conduct appropriately adjusted per-protocol analyses. We will use STATA 13.0 for all analyses. We also will examine a number of pre-specified subgroup analyses, in which we examine whether the intervention might be more effective among those SMI patients who are more likely to receive fragmented care or less likely to be adherent to complex treatment regimens, e.g., SMI patients with Medicaid versus those with commercial health insurance.

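### The SAP lets the data settle its primary model: covariate adjustment waits for an observed imbalance, and optional dropout weighting can overstate intervention-arm use where later use goes unrecorded

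*SAP*

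**What the plan says.** The SAP (Primary study outcome) defines the outcome as the proportion of the 12 follow-up months on medication. It is measured by medication counts at the four quarterly visits, supplemented by self-report and chart review. Participants eligible for both drugs at baseline are scored on days with both; those eligible for one are scored on days with that one.

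The SAP (Analysis of the primary study outcome) specifies an intention-to-treat regression. It adjusts for baseline covariates if an imbalance judged clinically meaningful appears, with no list or threshold. On dropout it says: "If necessary, we will adjust for selection bias due to loss to follow-up via inverse-probability weighting". It gives no trigger, no weight model and no rule for scoring time after the last visit.

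Related protocol text:

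- Section V, Obtaining Study Drugs: study drug is dispensed in three-month supplies, and "The study staff will pick up prescriptions from the pharmacy and provide to the subject during the study visit".
- Section IV, Control: "The RA/APRN pair will make no effort to alter or influence treatment or use of that treatment for subjects in the control arm".
- Section IV, Follow-up: the censoring events include those "who die, or who leave the study health care systems". The SAP does not say how these are scored.
- Section V, Additional Quality Checks: "We will use a standardized process for addressing imputation of missing values or reconciliation of different values". The process is not described.
- Section VI, Aim 2, the only place where the protocol describes weights for loss to follow-up: "Weighting will be based on baseline characteristics and for any given subject; the same weights will be applied to each repeated measure".

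**The concern.** Two choices in the primary model are left until data are in hand.

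The first is covariate adjustment. Drug-eligibility stratum is likely to predict the outcome, because taking two drugs on the same day is a stricter requirement than taking one. A covariate known in advance to matter should not wait for an observed imbalance.

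The second is weighting. Inverse-probability weighting lets retained participants stand in for those who leave, so it targets use had nobody left. In the intervention arm, leaving also cuts off the study supply. Weights built on baseline characteristics can correct for who leaves, but not for what leaving does to use afterwards. Control treatment has no such link to study visits. At stake is mainly the reported size of the effect; with a large true effect the test result may not change.

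Under Aim 2 the protocol commits to fixing its analysis before outcome data are examined, and adds: "Thus, we mitigate the potential for bias resulting from post-hoc choice of analysis or significance testing". Two undefined triggers in the primary analysis sit poorly with that intention.

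**Working it through.** The documents give no figure for dropout, for use after dropout, or for the share of participants in each eligibility stratum. What follows is therefore illustration on stated assumptions. From the documents come 150 per arm, control initiation below 15% (Power Calculations), three-month supplies and quarterly visits.

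**Assumed inputs.** d = dropout proportion; r = 70% use among retained intervention participants and among dropouts while supplied; a = intervention dropouts' use after supply ends; c = 15% control use, which borrows the initiation figure as a share of time.

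**Share of the year after supply ends (s).** A last visit at month 0, 3, 6 or 9 leaves 9, 6, 3 or 0 months unsupplied.

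- Month 0, 3 or 6 equally likely: s = (0.75 + 0.50 + 0.25)/3 = 0.50.
- Month 0, 3, 6 or 9 equally likely: s = (0.75 + 0.50 + 0.25 + 0)/4 = 0.375.

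**Overstatement of the intervention mean** = d × s × (r − a), in percentage points, if later use is not recovered:

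| d | a | s = 0.375 | s = 0.50 |
|---|---|---|---|
| 20% | 0 | 5.25 | 7.0 |
| 20% | 15% | 4.1 | 5.5 |
| 20% | 30% | 3.0 | 4.0 |
| 10% | 0 | 2.6 | 3.5 |
| 30% | 0 | 7.9 | 10.5 |

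If records recover later use for half the dropouts, these halve.

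**Effect on the between-arm difference.** If control dropouts keep using at 15%, the same figures apply. If their use stops at the same point, the bias is d × s × (r − a − c), which at d = 20% and a = 0 is 4.1 to 5.5 points.

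**Scale.** The standard error of the difference at means of 70% and 15% is at most √((0.70×0.30 + 0.15×0.85)/150) = 4.7 points, since a proportion with mean m has variance at most m(1 − m).

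**Do correct baseline weights remove it?** Suppose a marker held by half the arm raises dropout from 10% to 30% and lowers use from 85% to 55%, with no use after supply ends.

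- Retained mean: (0.5×0.9×0.85 + 0.5×0.7×0.55)/0.8 = 71.9%.
- Weighted mean: 0.5×0.85 + 0.5×0.55 = 70.0%.
- Actual, s = 0.50: 0.5×0.85×(1 − 0.05) + 0.5×0.55×(1 − 0.15) = 63.75%.
- Actual, s = 0.375: 0.5×0.85×(1 − 0.0375) + 0.5×0.55×(1 − 0.1125) = 65.3%.

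Weighting removes the 1.9 points due to who leaves; 4.7 to 6.3 points remain.

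**When does it vanish?** Take a covariate split 50/50, with use of 80% and 40% and loss of 10% and 40%, where leaving does not change use within a level. Retained participants use 0.48/0.75 = 64% and dropouts 0.12/0.25 = 48%. The weighted mean is 60% and true use is 60%, so there is no bias. The gap that matters is therefore between dropouts and retained participants with the same weighting covariates.

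**Covariates.** If a proportion p is eligible for one drug only, the 95% range of chance imbalance is ±1.96 × √(2p(1 − p)/150): 9.1 points at p = 20% and 11.1 at p = 40%. If use differs between strata by 10 to 20 points (assumed), the unadjusted difference shifts by up to 0.091 × 10 = 0.9 to 0.111 × 20 = 2.2 points, in either direction.

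**The case against.** A missed study visit need not mean missing outcome data. The SAP names self-report and chart review as sources. The protocol has staff check medical records about every three months (Section IV, Recruitment), provides for catch-up pill counts at clinic appointments, and collects claims data (APCD) from those who consent. Weighting might apply only to people who cannot be traced. This stands, and it makes the bias conditional: three things must hold together, namely that weighting is used, that later use is unrecorded, and that dropouts use less than comparable retained participants. Neither document, however, makes those records the rule for dropouts.

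Weighting is also an accepted way to estimate an intention-to-treat mean, and part of the dispute is a choice of estimand. That stands too. A reader might infer that the protocol rules weighting out, since it says for Aim 1 that "only an intent-to-treat (ITT) approach is relevant since whether or not subjects are on treatment is the outcome itself". But that sentence sets intention-to-treat against other analysis sets and does not address missing data. Nor does the power section's treatment of lost participants as not on care contradict the SAP; it is a sample-size assumption, though it shows that the coding was considered.

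The covariate point is modest. Chance imbalance is random error already reflected in the confidence interval, and the trigger is a baseline difference, not an outcome. The SAP's opening definition, which credits receipt of any prescribed medication, also sits uneasily with its both-drugs day count; the expectation that stratum is prognostic rests on the day count.

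Finally, scoring undocumented time as off treatment has its own error. With r = 70%, c = 15% and no documented later use, weighting is the less biased of the two only if intervention dropouts' later use exceeds (0.70 + 0.15)/2 = 42.5% when control dropouts keep using, or (0.70 − 0.15)/2 = 27.5% when they also stop.

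**Conclusion.** The concern holds in a limited form. Both triggers are undefined, so the primary model is not fixed in advance. Fixed adjustment for eligibility stratum is a better choice at almost no cost; the gain is a settled model and some precision, not removal of bias.

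Weighting, if used without recovering later use, overstates intervention-arm use when dropouts use less than retained participants with the same weighting covariates. Supply through study visits makes this plausible in the intervention arm. At 20% dropout, 70% retained use and none after supply ends, the overstatement is about 5 to 7 points, comparable to or larger than the standard error of the difference. It shrinks in proportion as records recover later use, and its effect on the difference depends on control dropouts. All of these inputs are assumed.

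A reader might go further and infer that lower use among dropouts is enough to bias weighting, or that the primary result will be biased. The documents support neither: a gap explained by the weighting covariates is what weighting corrects, and the SAP commits neither to weighting nor to a weight model.

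**What to change.** 1. Replace imbalance-triggered adjustment with fixed adjustment for baseline drug-eligibility stratum (both, statin only, angiotensin drug only) and clinic, stated before outcome data are seen.
2. In the primary intention-to-treat analysis include all randomised participants. Score time after the last visit by one rule in both arms, from chart review, self-report and, where released, APCD records. Count time without documented supply as not on treatment, keep the SAP's credit for later contraindication, and state how the protocol's censoring events are scored.
3. Report inverse-probability weighting, with a stated weight model, as a sensitivity analysis, beside one that carries forward control dropouts' last known use. Report bounds for the uncounted last supply: none taken and all taken.

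The change needs SAP wording and data already planned. Its costs are:

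- The estimate may be less favourable.
- Undocumented control use may be missed. At 20% dropout and 15% control use this is 0.20 × 0.375 × 0.15 = 1.1 points to 0.20 × 0.75 × 0.15 = 2.25 points. The upper figure assumes last visits at month 0, 3 or 6 with documentation ending at the last visit.
- If an uncounted last supply is scored as taken when it was not, credited use is too high by 0.20 × 0.25 × 0.70 = 3.5 points, or 0.20 × 0.25 = 5.0 at most.

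The last two lean toward the intervention; the carry-forward analysis and the bounds show how much they matter.
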